4.8 Safety Endpoints

- During scheduled follow-up assessments the percentage of patients in each arm of the trial with:
 - Hypokalaemia defined at various thresholds of serum potassium
 - <4.0mmol/L or<3.5mmol/L or <3.0mmol/L
 - Hyperkalaemia defined at various thresholds of serum potassium
 - >5.5mmol/L or >6.0mmol/L or >6.5mmol/L
 - Hypomagnesemia defined as <0.75mmol/L (<1.5mEq/L or <1.8mg/dL).
 - o eGFR
 - <30mL/min/1.73m² or <20mL/min/1.73m² or <10mL/min/1.73m²

 - Systolic blood pressure
 - <100mmHg or <90mmHg or<80mmHg

 - Heart rhythm
 - Sinus rhythm / atrial fibrillation / other rhythm
 - Doses of MRA, ACE inhibitors, Angiotensin Receptor Blocker and angiotensin-neprilysin inhibitors, diuretics and beta-blockers
 - Heart rate at each scheduled visit according to heart rhythm
- · Adverse reactions and Serious Adverse events related to
 - Hyper- or hypo-kalaemia or hypo-magnesaemia any record defined according to serum concentrations above
 - Renal failure defined as renal dialysis or death preceded by an eGFR <10ml/min/1.73m² (last measurement before death)
 - A decline in eGFR by >30% from baseline [24]
 - o A doubling in serum creatinine from baseline
 - Symptomatic Hypotension

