In the RALES trial that enrolled patients with advanced heart failure and eGFR >30mls/minute and a serum potassium ≤5.0mmol/L, the target dose of spironolactone was 50mg/day and the mean daily dose achieved at two years was 26mg/day (compared to 31mg/day of the corresponding placebo). The median increase in serum potassium was 0.3mmol/L in those assigned to spironolactone compared to placebo. Of 1,663 patient randomised, 5.6% of those assigned to placebo developed a serum potassium >5.5mmol/L compared to 19.0% of those assigned to spironolactone. The treatment benefit of spironolactone was "maintained at least until serum potassium exceeded 5.5mmol/L" (24) Few patients developed severe hyperkalaemia (serum potassium >6.0mmol/L) in either arm of the trial (1.2% versus 3.9%). No change in average blood pressure occurred and the median increase in serum creatinine was <10umol/L. Worsening renal function, defined as a fall in eGFR by >30% occurred in 7% of those assigned to placebo and 17% of those assigned to spironolactone and appeared unrelated to changes in blood pressure. However, the greatest benefit of spironolactone on morbidity and mortality was observed amongst those with the worst renal function (25). The RALES pilot trial, 5% of patients developed a serum potassium >5.5mmol/L compared to 20% of those assigned to 50mg/day of spironolactone and 24% of those assigned to 75mg/day after 12 weeks of

Version 5.0 22 July 2021 Page 19 of 82

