10. SAFETY AND OUTCOME REPORTING

10.1 Definitions

Term	Definition
Adverse Event (AE)	Any untoward medical occurrence in a participant to whom a medicinal product has been administered, including occurrences which are not necessarily caused by or related to that product.
Adverse Reaction (AR)	An untoward and unintended response in a participant to an investigational medicinal product which is related to any dose administered to that participant. The phrase "response to an investigational medicinal product" means
	that a causal relationship between a trial medication and an AE is at least a reasonable possibility, i.e. the relationship cannot be ruled out.
	All cases judged by either the reporting medically qualified professional or the Sponsor as having a reasonable suspected causal relationship to the trial medication qualify as adverse reactions. It is important to note that this is entirely separate to the known side effects listed in the SmPC. It is specifically a temporal relationship between taking the drug, the half-life, and the time of the event or any valid alternative aetiology that would explain the event.
Serious Adverse Event (SAE)	A serious adverse event is any untoward medical occurrence that: results in death is life-threatening requires inpatient hospitalisation or prolongation of existing hospitalisation results in persistent or significant disability/incapacity consists of a congenital anomaly or birth defect
	Other 'important medical events' may also be considered serious if they jeopardise the participant or require an intervention to prevent one of the above consequences.
	NOTE: The term "life-threatening" in the definition of "serious" refers to an event in which the participant was at risk of death at the time of the event; it does not refer to an event which hypothetically might have caused death if it were more severe.
Serious Adverse Reaction (SAR)	An adverse event that is both serious and, in the opinion of the reporting Investigator, believed with reasonable probability to be due to one of the trial treatments, based on the information provided.

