10.2 Operational reporting for (S)AEs

Adverse events (AEs) will be recorded, notified, assessed, reported, analysed and managed in accordance with the Medicines for Human Use (Clinical Trials) Regulations 2004 (as amended) and this protocol. All AEs occurring during the trial that are observed by the Investigator or reported by the participant will be recorded in the participant's medical records whether or not attributed to trial medication.

All adverse reactions must be recorded within the eCRF.

All Serious Adverse Events (SAEs) occurring during the trial must be recorded in the eCRF.

The following are not considered be to be SAEs for the purposes of this trial.

- Routine treatment or monitoring of heart failure not associated with deterioration in heart failure.
- Treatment which was elective or pre-planned, for a pre-existing non-cardiac condition not associated with any deterioration in heart failure, e.g. pre-planned hip replacement operation which does not lead to further complications.
- Treatment on an emergency, outpatient basis for an event not fulfilling any of the definitions of serious as given above and not resulting in hospital admission.
- Admissions for social reasons not associated with a deterioration of heart failure.

All SAEs will be reported to the IDMC and analysed as part of the final trial results.

Full details of SAEs will be recorded in the electronic Case Report Form. The following information will be collected:

- full details in medical terms and a case description
- event duration (start and end dates, if applicable)
- action taken
- outcome
- · seriousness criteria
- causality (i.e. relatedness to trial drug / investigation), in the opinion of the investigator
- if related, whether the reaction would be considered expected or unexpected.

Any change of condition or other follow-up information should be added to the eCRF as soon as it is available or at least within 24 hours of the information becoming available. Events will be followed up until the event has resolved or a final outcome has been reached.

Assessment of Adverse Events

All adverse events must be assessed for seriousness. All SAEs must also be assessed for severity, causality and expectedness with reference to this protocol and the Reference Safety Information (RSI).

Version 5.0 22 July 2021 Page 54 of 82

Assessment of seriousness

An adverse event will be considered serious if it:

- results in death
- is life threatening

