10.3 Serious Adverse Events (Sponsor reportable events)

Patiromer, spironolactone and eplerenone have well-understood safety profiles. Previous clinical trials have shown the combination of drugs to be well-tolerated (12). However, when the IMPs are used in combination there remain potential concerns regarding the effects of the IMP(s) on serum potassium.

In addition, participants in this trial are expected to have high rates of hospitalisations, cardiovascular events and death due to cardiac disease and related co-morbidities that are unlikely to be attributable to treatment with the trial IMP(s). These events will, however, inform the primary and secondary endpoints of the trial and will be subject to monitoring by the Data Monitoring Committee. As such these event will be recorded within the eCRF as per section 9.2.

Where the medicines are used in combination, the principle concern is changes in serum potassium and/or magnesium. For the purposes of pharmacovigilance, safety reporting will focus on the occurrence of hypokalaemia, hyperkalaemia, hypomagnesaemia, and events associated with these conditions, in particular potentially harmful renal insufficiencies.

Monitoring of non-reportable events

Non-reportable events will be monitored during the study. If deemed necessary, an initially non-reportable event may be added to the list of events reported to Sponsor. The process for this will be documented separately.

The following will be recorded on the eCRF as Serious Adverse Events and will be subject to expedited reporting to the sponsor:

- Any SAE that is considered, in the Investigator's opinion, related to the administration of any of the IMPs used in the trial, whether individually or in combination.
- Any incidence of an acute kidney injury meeting the criteria of a serious adverse event.
- Renal failure associated with a requirement for renal dialysis/ultrafiltration; and deaths associated with renal failure as evidenced by a preceding eGFR of 10ml/min/L/1.73m²
- SAEs associated with one of the following electrolyte disturbances
 - Severe hypokalaemia defined as serum potassium <3.0mmol/L
 - Severe hyperkalaemia defined as a serum potassium> 6.5mmol/L
 - Severe hypomagnesaemia defined by a serum magnesium <0.5mmol/L

Suspected Unexpected Serious Adverse Reactions (SUSARs)

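### Section 4.8 gives the relative renal safety measures (eGFR fall above 30%, creatinine doubling) no laboratory-based count, because it lists them only under adverse reactions and SAEs

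*Protocol*

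**What the plan says.** Protocol section 4.8 has two blocks.

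- The first opens "During scheduled follow-up assessments the percentage of patients in each arm of the trial with" and then gives laboratory and vital-sign thresholds. Its only eGFR items are absolute: below 30, 20 or 10 mL/min/1.73m².
- The second opens "Adverse reactions and Serious Adverse events related to". It is the only part of 4.8 that contains "A decline in eGFR by >30% from baseline [24" and the doubling of serum creatinine. Within this block, the potassium and magnesium item is worded to take in any record meeting the serum thresholds. The two renal items carry no such wording.

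What reaches the second block is set in section 10.

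- Section 10.2 states: "All adverse reactions must be recorded within the eCRF". SAEs must also go into the eCRF. Other adverse events are required only in the medical record.
- Under section 10.1 an adverse reaction is a case "judged by either the reporting medically qualified professional or the Sponsor" to have a suspected causal link.
- On assessment, section 10.2 requires every adverse event to be assessed for seriousness, then adds: "All SAEs must also be assessed for severity, causality and expectedness". It names no causality assessment for non-serious events.
- Section 10.3 makes the following reportable whatever its cause: "Any incidence of an acute kidney injury meeting the criteria of a serious adverse event".

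Treatment is open-label (section 8.5).

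**The concern.** Section 3 recognises renal dysfunction as a risk of MRA, and the strategy under test aims at higher MRA doses. A relative fall in eGFR is therefore a natural safety measure. Section 3 itself reports it for an earlier spironolactone trial in advanced heart failure, where renal deterioration, "defined as a fall in eGFR by >30% occurred in 7% of those assigned to placebo and 17% of those assigned to spironolactone". That definition rests on eGFR and does not mention attribution.

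In section 4.8 the same measure sits behind a reporting step. A non-serious fall that crosses no absolute cut-off enters the planned count mainly when someone who knows the allocation reports it as an adverse reaction. Sites may differ in how readily they do so. They may also treat the arms differently, for example by suspecting the drug more at higher doses, or by regarding a fall as expected and not reporting it. What is at stake is a clean comparison between arms of one renal safety endpoint.

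**Working it through.** The plan states no figure on this point, so there is none to reproduce. The check has three parts.

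**1. Which falls does the scheduled-visit list miss?**

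Inputs: the highest absolute cut-off is 30 (section 4.8); patients with eGFR below 30 are excluded (section 7.2); the relative criterion is a fall of more than 30% (section 4.8).

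For baseline B and fractional fall f, the follow-up value is B × (1 − f). It stays at or above 30 if f ≤ 1 − 30/B. For some f above 0.30 to qualify, B must exceed 30/0.70 = 42.9.

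| Baseline B | After an exact 30% fall (0.70 × B) | Largest fall staying at or above 30 (1 − 30/B) | Falls above 30% that cross no cut-off |
|---|---|---|---|
| 40 | 28.0 | 25.0% | none |
| 42 | 29.4 | 28.6% | none |
| 43 | 30.1 | 30.2% | 30% to 30.2% |
| 45 | 31.5 | 33.3% | 30% to 33.3% |
| 50 | 35.0 | 40.0% | 30% to 40% |
| 60 | 42.0 | 50.0% | 30% to 50% |
| 75 | 52.5 | 60.0% | 30% to 60% |
| 90 | 63.0 | 66.7% | 30% to 66.7% |

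The absolute cut-offs do not stand in for the relative measure. A change from 60 to 40 is a fall of 20/60 = 33.3% and crosses none of them. A change from 32 to 29 is a fall of 3/32 = 9.4% and counts as below 30.

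**2. The same check for creatinine doubling.**

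Assumption: eGFR varies as creatinine to the power −k, with k between 1.0 and 1.2. After doubling, eGFR is B × 2^(−k). It stays at or above 30 if B ≥ 30 × 2^k.

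- k = 1.0: B ≥ 60.0
- k = 1.2: B ≥ 68.9

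Section 9.12 expects most if not all patients to have renal dysfunction, so the doubling gap may concern few.

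**3. How can a non-serious fall that crosses no cut-off be counted?**

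- As an adverse reaction (sections 10.1 and 10.2). This needs a suspected link to a trial drug, judged by the site or the Sponsor.
- As a flagged event. Section 10.4 asks the principal investigator to flag, and the chief investigator to confirm, events of special interest or potential endpoints, using the protocol's definitions. The protocol does not say that the two renal items are covered.
- As a serious event. Section 10.2 treats an event of special interest as serious and refers back to a definition, but none precedes it. The list in section 11.5 names renal failure, not a relative fall.
- From laboratory values. The data would exist: creatinine is scheduled after randomisation on days 3, 5, 7, 14, 30 and 60 and at months 3, 6, 9 and 12, which is 6 + 4 = 10 values in the first year (sections 8.1.1, 8.1.2 and 8.7.3). Neither document says that the two measures will be derived from them.

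The first route is the only one clearly laid down. The fourth is available but not planned.

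**The case against.** The strongest reply is that the items were meant as laboratory criteria all along. Both are numerical changes from baseline that cannot be identified without serial creatinine. The list layout in 4.8 is partly garbled in the text available, and a laboratory criterion does occur under the same heading, for potassium and magnesium. This may well be the intent. If so, the protocol still does not say it, and the fix only writes it down.

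A reader might infer that such a fall counts only if it is judged drug-related, with no other way in. The documents do not support that. The flagging duty in section 10.4 and the special-interest criterion in section 10.2 are possible routes, though undefined for these items. The attribution bar in section 10.1 is also low: a link need only be reasonably possible, in the sense of not being excluded. MRA is a trial drug in both arms, so a fall on MRA would seldom fail that test. The causality categories in section 10.2 are stricter, asking whether the trial drug is the most likely cause, so the protocol is not consistent on the bar.

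A reader might also treat the 7% and 17% as a benchmark that the trial could no longer be set against. Section 3 gives them as background, no such comparison is planned, and both measures remain derivable from the creatinine collected.

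The SAP's silence is weak evidence. Section 11.8 defers detail to the SAP, but the only SAP was written after closure with four participants randomised and drops formal analysis (SAP 1.6.1 and 1.6.3).

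Finally, the gap is limited. Section 1 describes severely congested patients as usually having moderate to severe renal impairment, and nothing is missed below a baseline of about 43. On the other side, section 8.4 minimises on eGFR above or below 45, so patients above that level were anticipated.

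**Conclusion.** The point holds, and it is minor. As written, section 4.8 gives no laboratory-based count of non-serious relative renal decline that stays at or above eGFR 30. That count depends mainly on adverse reaction reporting in an open-label trial, so it could be incomplete or could differ by arm.

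The gap is confined to baselines of about 43 or more for the 30% fall, and about 60 to 69 or more for creatinine doubling under the stated assumption on k. Serious acute kidney injury lies outside it.

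No number of missed events and no direction of bias can be claimed. The documents give neither a baseline eGFR distribution nor a reporting rate. The 7% and 17% cannot be carried over to supply one, because both arms here may receive MRA.

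The defect is in the planned endpoint definition, not in data collection. It does not affect the report of the closed trial: SAP 2.6 already lists follow-up laboratory values for the four randomised participants, and the laboratory set in SAP 2.4 includes calculated eGFR.

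**What to change.** Add two items to the scheduled-visit list in section 4.8: eGFR decline of more than 30% from baseline, and doubling of serum creatinine from baseline. State that both are derived from measured creatinine relative to the randomisation value, for every randomised patient, by arm, at each visit and as having ever occurred, whether or not an adverse reaction or SAE was reported. Keep the adverse reaction and SAE count as a separate line.

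The cost is two bullets and two derived variables from creatinine already scheduled at every follow-up visit. No new data or visits are needed. The closed trial's report needs no change; the edit matters if this protocol is reused.

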5. TRIAL DESIGN

A Phase IV, registry-based, randomised (1:1), open-label trial investigating whether administration of patiromer enables use of higher doses of mineralocorticoid antagonists and thereby improves the severity of congestion and patients' well-being, morbidity and mortality for patients with heart failure, worsening congestion and hyperkalaemia.

Hospitalisations and mortality will be adjudicated independently blind to treatment allocation.

6. TRIAL SETTING

This is a multi-centre trial that will be conducted in approximately 100 UK NHS Trusts/Boards responsible for managing patients with heart failure who have sufficiently severe manifestations of congestion that they are being considered for intravenous diuretic therapy.

Principal investigators will be experts in the management of heart failure and may either be a) doctors or b) nurses/pharmacists working under the supervision of a doctor with expertise in the management of heart failure. The TSC will review the curricula vitae of all proposed principal investigators to ensure they are suitably qualified and experienced to conduct the trial with adequate support. Either a principal investigator who is medically qualified or a designated medical practitioner on the delegation log will verify that all inclusion/exclusion criteria have been met. Doctors and appropriately qualified non-medical prescribers who have been delegated this task by the local principal investigator may prescribe MRA and patiromer as described in this protocol and as randomly assigned, provided this is in accordance with local policies and procedures.

Participants are typically 'known' to heart failure services and are hospitalised or require intensive management either as day-cases or by community heart failure services.

Participants will be identified from primary or secondary care services, including hospital wards and clinics and community heart failure services. The precise set-up of heart failure services/pathways will vary according to locality. If a patient moves away from their original trial site and they can attend visits at an alternative trial site they may continue with their randomised treatment allocation. Otherwise, patients will be withdrawn from trial follow-up visits and those assigned to receive patiromer will revert to standard care. These patients will continue to be followed for hospitalisations and deaths by the investigators until the end of the trial or by record linkage in the extended follow-up phase.

7. PARTICIPANT ELIGIBILITY CRITERIA

7.1 Inclusion Criteria

For the Screening Log (no follow-up envisaged nor linkage to electronic medical records)

- 1. ≥18 years
- 2. Heart failure in the investigators opinion (new onset or decompensated chronic heart failure)
- 3. Planned to receive >80mg/day of furosemide or equivalent* (IV, SC, or oral) in the next 24 hours.
- 4. Worsening symptoms & signs of congestion in the prior10 days requiring at least **one** of the following:
 - a) hospitalisation
 - b) administration of intravenous diuretics
 - c) an increase in the dose of loop diuretic by at least 40mg/day of furosemide (or equivalent**) to a total of at least 80mg/day of furosemide (or equivalent*)
 - d) addition of a thiazide diuretic to treatment with a loop diuretic

Version 5.0 22 July 2021 Page 25 of 82

- * a dose of 80mg/day of furosemide is considered equivalent to 2mg/day of bumetanide or 20mg/day of torasemide.
- ** a dose of 40mg/day of furosemide is considered equivalent to 1mg/day of bumetanide or 10 mg/day of torasemide.

For the Consented Registry (with linkage to electronic medical records)

- 1. Fulfils the criteria for the screening log
- 2. Able and willing to provide written informed consent for registry participation

For Randomised Trial Run-in

- 1. Fulfils criteria for the consented registry
- 2. Clinical diagnosis of heart failure for at least 4 weeks
- 3. Congestion as shown by at least one of the following:
 - a) Peripheral oedema
 - b) Raised venous pressure
 - c) Inferior vena cava diameter >20mm
- 4. Cardiac dysfunction documented by at least **one** of the following in the previous three years:
 - a) A LVEF<50% or a report of moderate or severe left ventricular dysfunction
 - b) Left atrial diameter >3.0cm/m2 (body surface area)
 - c) Elevated BNP or NT-proBNP
 - i. BNP >150ng/L if in sinus rhythm or >450ng/L if not in sinus rhythm
 - ii. NT-proBNP >500ng/L if in sinus rhythm and >1500ng/L if not in sinus rhythm
- 5. Able and willing to provide written informed consent for the randomised trial

For Randomisation

- 1. Serum potassium >5.0mmol/L
 - Patients with a serum potassium >5.0mmol/L may be randomised immediately unless they have severe hyperkalaemia requiring, in the investigators opinion, intravenous treatment or a potassium binding agent.
 - Severe hyperkalaemia should be managed according to the UK Renal Association guidelines of 2014 (https://renal.org/wp-content/uploads/2017/06/hyperkalaemia-guideline-1.pdf).
 Participants may be reconsidered for the trial once such interventions are no longer considered necessary.
 - Patients with a serum potassium ≤5.0mmol/L should be initiated on spironolactone or have the
 dose increased up to 100mg/day and randomised only if serum potassium exceeds 5.0mmol/L.
 Those intolerant of or unwilling to take spironolactone should be offered eplerenone titrated to
 a maximum dose of 50mg/day.
 - A run-in period of up to 35 days is permitted (the run-in period will usually occur during hospitalisation or a course of day-care or intense management).
- 2. After ingestion of a test-dose of patiromer,
 - a) the patient is willing to continue in the trial
 - b) the investigator considers the patient can follow instructions on preparing patiromer

